10.1.2. Blood sample collection for PBMC isolation

Only patients allocated to pembrolizumab treatment will be asked to provide blood for PBMC (Peripheral Blood Mononuclear Cell) isolation. The sites will be geographically determined in order for the sample to be couriered to the central c-TRAK TN laboratory within an appropriate timeframe for processing, eligible PBMC sites will be confirmed on a case by case basis. Where possible, blood for PBMC isolation should be collected in the morning to allow for prompt shipment and processing within the recommended timeframe.

Patients receiving pembrolizumab treatment at the designated PBMC sites will have blood samples for PBMC isolation taken on day 1 of cycle 1 and day 1 of cycle 3.

11. ASSESSMENTS FOR PEMBROLIZUMAB TREATMENT GROUP

The schedule of assessments for the pembrolizumab treatment group shows all required trial assessments in table form (see section 11.7). All blood and tissue samples should be collected according to the instructions provided in the c-TRAK TN Investigator Laboratory Manual.

The patient should start pembrolizumab treatment as soon as possible and within a maximum of 4 weeks of allocation to the pembrolizumab treatment group being confirmed by the ICR-CTSU.

11.1. Pre-treatment assessments

The following pre-treatment assessments should be conducted once written informed consent to start **pembrolizumab has been obtained** from the patient and after the treatment eligibility checklist has been completed by the principal investigator (or designated investigator) and submitted to ICR-CTSU. The pre-treatment assessments should be done prior to the first dose of pembrolizumab treatment as below.

Assessments to be conducted within 4 weeks prior to starting treatment:

- Imaging to assess for macroscopic disease (using same modality as diagnosis). For example patients
 screened with CT and bone scan at diagnosis should have both repeated, or patients screened with
 FDG PET-CT at diagnosis should have a FDG PET-CT repeated. Patients who did not have imaging at
 diagnosis should have imaging in line with local guidelines for high risk disease
- ECG
- Demographics and baseline conditions

Assessments to be conducted within 72 hours prior to the first dose of pembrolizumab:

- Safety blood tests: clotting (INR or PT/ aPTT), haematology (ANC, platelets, haemoglobin), biochemistry; hepatic function (bilirubin, ALT, AST, ALP and GGT), renal function (serum creatinine or estimated GFR (using Cockcroft-Gault)), thyroid function (T3, T4, TSH), glucose (random)
- Urinalysis
- Female patients of childbearing potential should have a negative urine or serum pregnancy test. If the urine test is positive or cannot be confirmed as negative, a serum pregnancy test will be required
- Concomitant medication review
- Full physical examination (ECOG performance status, vital signs, height and weight)

- Research blood samples for ctDNA analysis:
 - o 2 x 10ml collected in ctDNA preservation tubes
- Research blood sample for PBMC (peripheral blood mononuclear cell) isolation (PBMC sites only)
 - 3 x 10ml collected in heparin tubes, to be couriered as soon as possible after collection, as per the c-TRAK TN Investigator Laboratory Manual

11.2. Assessments during pembrolizumab treatment

Treatment with pembrolizumab will continue for a maximum of 12 months. Pembrolizumab should be administered on Day 1 of each cycle after all assessments have been completed as detailed below and in the schedule of assessments for pembrolizumab treatment. Pembrolizumab treatment may be administered up to 72 hours before or after the scheduled Day 1 of each cycle. Refer to section 17 for further information regarding dosing interruptions.

Patients should be followed-up for disease recurrence in line with standard practice every 6 months (+/- 1 month to coincide with a treatment cycle) from the start of ctDNA surveillance.

11.3. Prior to each cycle (cycle 2 onwards)

Please see section 11.1 for assessments required prior to the first dose of pembrolizumab (i.e. cycle 1 only). The following assessments should be conducted within 72 hours prior to each cycle (from cycle 2 onwards) of pembrolizumab:

- Concomitant medication review
- Review of adverse events
- Full physical examination (including weight at cycles 4, 8, 12 and 16 only, ECOG performance status, vital signs)
- Safety blood tests: clotting (INR or PT/ aPTT), haematology (ANC, platelets, haemoglobin), biochemistry; hepatic function (bilirubin, ALT, AST, ALP and GGT), renal function (serum creatinine or estimated GFR (using Cockcroft-Gault)), thyroid function (T3, T4 TSH), glucose (random)
- Urinalysis
- ECG (only if clinically indicated)
- Research blood samples for ctDNA analysis:
 - o 2 x 10ml collected in ctDNA preservation tubes taken pre-dose on each cycle
- Research blood samples for PBMC isolation pre-dose **ONLY on cycle 3** (PBMC sites only)
 - 3 x 10ml collected in heparin tubes, to be couriered same day as per the c-TRAK TN Investigator Laboratory Manual.

11.4. Assessments at discontinuation of pembrolizumab treatment

On the **day of the last administration of pembrolizumab treatment** (or at the next planned visit if treatment discontinuation occurs between cycles), the following assessments should be conducted:

- Concomitant medication review
- Review of adverse events
- Full physical examination, ECOG performance status, vital signs
- Safety Blood tests: clotting (INR or PT/ aPTT), haematology (ANC, platelets, haemoglobin), biochemistry (hepatic function (bilirubin, ALT, AST, ALP and GGT), renal function (serum creatinine or estimated GFR (using Cockcroft-Gault)), thyroid function (T3, T4 TSH), glucose (random)
- Urinalysis
- Research blood samples for ctDNA analysis (at treatment discontinuation only):
 - o 2 x 10ml collected in ctDNA preservation tubes

Approximately **30 days after the last administration of pembrolizumab treatment or before initiation of a new anti-cancer treatment, whichever comes first,** the following assessments should be conducted:

- Review of adverse events
- Safety Blood tests: clotting (INR or PT/ aPTT), haematology (ANC, platelets, haemoglobin), biochemistry (hepatic function (bilirubin, ALT, AST, ALP and GGT), renal function (serum creatinine or estimated GFR (using Cockcroft-Gault)), thyroid function (T3, T4 TSH), glucose (random)

11.5. Follow-up assessments post pembrolizumab treatment

For 12 months after the completion of pembrolizumab treatment, the following assessments should be conducted:

- Research blood samples for ctDNA analysis taken every 3 months from start of ctDNA surveillance:
 - o 2 x 10ml collected in ctDNA preservation tubes at each visit
- Disease recurrence (every 6 months, +/- 1 month, from start of ctDNA surveillance)

Following this, all patients should continue to be followed up in line with standard practice at 6 monthly intervals (+/- 1 month) until disease recurrence unless the patient specifically withdraws consent for follow up (see section 12) or until the ICR-CTSU confirms to the recruiting sites that no further follow up is required. This may be done by a telephone call with the patient. A recurrence tumour tissue sample should be provided at relapse for each patient who has tissue available from a biopsy taken routinely as part of standard patient care.

Patients who stop pembrolizumab before completing 12 months of therapy, and without recurrence, should have research blood samples taken 3 monthly for a further 12 months, calculated from the start of ctDNA surveillance.

11.6. Discontinuation from pembrolizumab treatment

A patient may discontinue from pembrolizumab treatment at any time at their own request, or they may be discontinued at the discretion of the Principal Investigator (or designated investigator). Reasons for discontinuation may include:

- Disease recurrence
- Unacceptable toxicity

• Pregnancy

Patients who discontinue treatment for reasons other than disease recurrence should continue to be followed up as described in section 11.5. Patients who discontinue pembrolizumab treatment due to disease recurrence should be assessed as described in section 13 and then treated for disease recurrence as per local guidelines, no further blood samples for ctDNA analysis should be collected for these patients, and no further follow up is required.

ICR-CTSU

11.7. Schedule of assessments for pembrolizumab treatment group

	Pre-treatment	Pembrolizumab Treatment Cycles			Cvcles	End of Treatment		Post-Treatment		
	Screening					C4-	Discontinuation	Safety Follow-up	-	Up Visits
	Day -28 to Day-1	С	1	C2	C3	C17	(max 12 months)	, ,		
									Every 3 months	Every 6 months
									from the start of	from start of
									ctDNA	ctDNA surveillance
									surveillance for	until disease
				- 1					12 months	recurrence
Duranda and Anna and an		D1		D1 ¹	D1 ¹ -	D41	At the set	30 days post	following	(+/- 1 month)
Procedures & Assessments:		-72	D1	-			At time of Discontinuation	discontinuation ²	treatment discontinuation ³	
		hrs	D1	-	72hrs				discontinuation	
Written informed consent ⁴	v	1	1	Admi	nistrati	ve Proce	edures			
Inclusion/exclusion criteria	X X									
	X									
Demographics and medical history										
Concomitant medication review	X	Х		Х	Х	Х	Х			
Eligibility confirmation to ICR-CTSU	Х									
Full shorted an estimation 5	v.	V		1	1	-	essments			
Full physical examination ⁵	X	Х		Х	Х	Х	Х			
Imaging ⁶	Х			v	v	v	V	V		
Review adverse events Pembrolizumab administration ¹			х	X X	X X	X X	Х	Х		
Disease recurrence ⁷			^	^	^	^				Х
Disease recurrence	Laborato	ny Proc	oduros	//	monts: a	nalvsis	performed by LOCAI	laboratory		^
Pregnancy test – urine or serum β -	X	ITY FICE	euures	A336331	nents. a	111019515				
HCG^8	~									
Clotting ⁹	Х	Х		Х	Х	Х	Х	Х		
Haematology ⁹	Х	Х		Х	Х	Х	Х	Х		
Biochemistry ⁹	Х	Х		Х	Х	Х	Х	Х		
Thyroid function ⁹	Х	Х		Х	Х	Х	Х	Х		
Hepatic function ⁹	Х	Х		Х	Х	Х	Х	Х		
Renal function ⁹	Х	Х		Х	Х	Х	Х	Х		
Glucose ⁹	Х	Х		Х	Х	Х	Х			
ECG	Х									
Urinalysis	Х	Х		Х	Х	Х	Х			
				r	arch Blo	r				
Blood sample for ctDNA analysis ¹⁰		Х		Х	Х	Х	Х		Х	
Blood sample for PBMC isolation ¹¹		Х			Х					

ICR-CTSU

- 1. Day 1 of each treatment cycle is the day of pembrolizumab treatment administration. All assessments, including sample collection, should be performed within 72 hours prior to day 1. Each cycle should be 21 days in length. Day 1 of each cycle should be planned for 21 days (+/- 72 hours) from day 1 of the previous cycle.
- 2. SAEs that occur within 90 days of the end of treatment and before initiation of a new anti-cancer treatment, whichever comes first, should be reported, followed and recorded.
- 3. Follow up bloods for patients who complete pembrolizumab or discontinue prematurely should be taken every 3 months in line with the start of ctDNA surveillance. For example if a patient goes on to receive treatment due to a positive ctDNA result at the 12 month ctDNA surveillance blood sample and then completes the full 12 months of pembrolizumab treatment, bloods will be taken at month 27, 30, 33, 36 and 39 from the start of ctDNA surveillance, and if a patient discontinues at month 7 bloods would be taken at month 21, 24, 27, 30 and 33 from start of surveillance
- 4. Written informed consent must be obtained from the patient prior to pre-treatment assessments being conducted.
- 5. Full physical examination includes height (prior to first dose of pembrolizumab only), weight (required prior to first dose of pembrolizumab and cycles 4, 8, 12 and 16 only), ECOG performance status and vital signs (heart rate, blood pressure).
- 6. Consent for imaging is included in registration PIS and ICF following implementation of protocol v6.0 onwards. Patients should undergo imaging immediately upon confirmation of a ctDNA positive result. The same investigations conducted as part of staging for the original primary breast cancer should be repeated. Patients who did not have imaging at diagnosis should have imaging in line with local guidelines for high risk disease.
- 7. Patients should be followed-up in line with standard practice every 6 months (+/- 1 month) from start of ctDNA surveillance. During post treatment follow up this can be conducted as a telephone call to the patient. Patients should be asked about relapse of breast cancer or other change in medical history. A recurrence tumour tissue sample should be provided at relapse for each patient who has tissue available from a biopsy taken routinely as part of standard patient care.
- 8. Pregnancy test should be done within 72hrs of first administration of pembrolizumab treatment.
- 9. With the exception of the end of treatment assessments, safety blood tests should be conducted within 72 hours prior to each cycle of pembrolizumab.
- 10. During pembrolizumab treatment, 2 x 10ml of blood should be collected in ctDNA preservation tubes on day 1 (pre-dose) of each cycle and until completion or withdrawal of pembrolizumab treatment. For 1 year after the administration of the last dose of pembrolizumab, 2 x 10ml of blood should be then collected every 3 months (+/- 2 weeks).
- 11. Research blood sample only at PBMC sites. 3 X 10ml heparin tubes, to be couriered to lab same day.

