3.2.1. Pembrolizumab treatment group

If a patient is allocated to the pembrolizumab treatment group, the treating team will be informed by ICR-CTSU. If the patient is receiving adjuvant capecitabine or radiotherapy, they will be offered the option to join the therapeutic trial either by switching treatment from capecitabine to pembrolizumab, or commencing pembrolizumab in combination with radiotherapy. If the patient confirms their consent to receive trial treatment (including switching their treatment from capecitabine to pembrolizumab) staging scans should be done to detect for evidence of macroscopic disease, prior to commencing pembrolizumab. If macroscopic disease is detected, the patient will not receive pembrolizumab treatment and will instead receive standard treatment for recurrent disease outside of the c-TRAK TN trial. If there is no evidence of macroscopic disease, the patient should commence treatment with pembrolizumab treatment (200mg given intravenously every 3 weeks) for up to a maximum of 12 months or until unacceptable toxicity or withdrawal of the patient's consent for any reason (see section 11.6). No further imaging will be performed after commencing pembrolizumab unless clinically indicated, in which case local procedure should be followed. Patients who are diagnosed with disease recurrence must stop pembrolizumab, and should receive standard treatment for recurrent disease outside of the c-TRAK TN trial. Patients who present with isolated lymphadenopathy may continue pembrolizumab until relapse is confirmed, and should be managed as per section 13.1.

Patients who are allocated to pembrolizumab but do not wish to commence pembrolizumab treatment (including switching treatment from capecitabine to pembrolizumab), will not enter the therapeutic component of the c-TRAK TN trial and if agreed should instead continue with 3 monthly ctDNA surveillance. Blood samples for ctDNA analysis should continue to be collected during and after pembrolizumab treatment as described in section 11. The results of these ctDNA analyses will not be reported to the treating team or patient.

3.2.2. **Observation group (continued blinded ctDNA surveillance – prior to protocol v6.0)**

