9.1. Procedure for obtaining informed consent for pembrolizumab treatment

Patient consent for starting pembrolizumab treatment must be obtained following confirmation from ICR-CTSU that the patient has been allocated to the pembrolizumab treatment group.

The Principal Investigator (or designated investigator) must ensure that each patient is fully informed about the nature and objectives of the trial and possible risks associated with pembrolizumab treatment.

The patient should be given the current ethics approved **c-TRAK TN patient information sheet for pembrolizumab treatment** for their consideration. Patients should only be asked to confirm consent to the trial after they have had sufficient time to consider the implications of a positive ctDNA result, the rationale for accepting pembrolizumab treatment and had the opportunity to ask any further questions.

No further protocol required assessments, other than those required as part of the ctDNA surveillance and standard patient care, should be conducted until the **c-TRAK TN consent form for pembrolizumab treatment** has been signed and dated by both the patient and the investigator at the recruiting site.

Confirmation of the patient's consent and the informed consent process should be documented in the patient's medical notes. A copy of the signed consent form should be provided to the patient and the original retained in the investigator site file, which must be made available for verification by ICR-CTSU trial staff or for regulatory inspection at any time.

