9.2. Eligibility criteria for pembrolizumab treatment group

Patients allocated to the pembrolizumab treatment group will be considered eligible to start pembrolizumab treatment only if they fulfil all the inclusion and none of the exclusion criteria listed below. Eligibility should be checked and pre-treatment assessments carried out once allocation to the pembrolizumab treatment group has been confirmed by ICR-CTSU and patient consent to start treatment has been obtained.

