9.3. Procedure for confirming patient eligibility to start pembrolizumab treatment

If the patient is confirmed eligible to start pembrolizumab treatment, then treatment should commence within a maximum of 4 weeks of the date when the recruiting site was first notified about the treatment allocation. For patients who are switching treatment from capecitabine to pembrolizumab, a washout period of 4 weeks must be observed prior to starting trial treatment. This period may be extended if delays are

encountered for practical reasons including those caused by the COVID 19 pandemic and the patient remains eligible per protocol, please discuss such cases with the ICR-CTSU trial team.

Patients who are ineligible to start treatment due to macroscopic disease identified on pre-treatment imaging will not receive treatment within the c-TRAK TN trial and will instead be treated as per local guidelines for metastatic disease/recurrence. No further blood samples for ctDNA analysis should be collected.

Patients who do not meet the eligibility criteria (for reasons other than disease recurrence) or do not wish to receive pembrolizumab treatment, should continue to have bloods taken for ctDNA surveillance every 3 months for up to 2 years from starting ctDNA surveillance. Patients should then be followed up for disease recurrence detection as described in section 11.5.

The **pre-treatment eligibility checklist** must be completed for all patients allocated to pembrolizumab treatment to confirm patient consent and eligibility and the planned start date of treatment (where applicable). The pre-treatment eligibility checklist should be completed within 4 weeks of when the recruiting site was first notified about the treatment allocation. Written confirmation that eligibility has been assessed by an investigator and confirmation of the patient's consent and the informed consent process should be documented in the patient's medical records.

For patients confirmed eligible, pembrolizumab treatment should commence as soon as possible and within a maximum of 4 weeks from when the recruiting site was first notified about the treatment allocation. As stated above, for patients receiving capecitabine a 4 week washout is required. The trial assessments that should be performed before, during and after pembrolizumab treatment are detailed in section 11.

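### Note 6 of 11.7 orders the staging scan on a positive ctDNA result, but 3.2.1 and 11.1 hold it until consent to pembrolizumab, so allocated patients who decline may go unscanned for a secondary endpoint

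*Protocol*

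**What the plan says.** **Scan on the ctDNA result.** Protocol 11.7, note 6: "Patients should undergo imaging immediately upon confirmation of a ctDNA positive result". The same note gives the basis for consent: "Consent for imaging is included in registration PIS and ICF following implementation of protocol v6.0 onwards".

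**Scan after consent to pembrolizumab.**

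- 3.2.1: "If the patient confirms their consent to receive trial treatment (including switching their treatment from capecitabine to pembrolizumab) staging scans should be done".
- 11.1 lists imaging for macroscopic disease among the pre-treatment assessments. These follow written consent to start pembrolizumab and also come "after the treatment eligibility checklist has been completed by the principal investigator (or designated investigator) and submitted to ICR-CTSU".
- 9.2 puts the pre-treatment assessments at the point when allocation is confirmed and "patient consent to start treatment has been obtained". The last paragraph of the introduction to section 9 has the same order.

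**Texts that lean the same way but are less clear.** 9.1 says "No further protocol required assessments, other than those required as part of the ctDNA surveillance and standard patient care, should be conducted until the" treatment consent form is signed. Note 4 of 11.7 says "Written informed consent must be obtained from the patient prior to pre-treatment assessments being conducted", without naming the form.

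**Patients who decline.** 9.3 says that those who "do not wish to receive pembrolizumab treatment, should continue to have bloods taken for ctDNA surveillance every 3 months". Neither 9.3 nor 3.2.1 mentions a scan for them.

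**The endpoint.** 19.3.2 defines the rate of overt metastases, by scan at the time of first ctDNA detection, in the patients allocated to pembrolizumab. Allocation follows the ctDNA result and precedes the treatment consent.

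**The concern.** The two rules cannot both be followed for a patient who is ctDNA-positive, allocated to pembrolizumab and then declines. Note 6 has the scan done before she decides. Under 3.2.1 and 11.1 the condition for the scan is never met, and she returns to blood sampling every 3 months. Patients on capecitabine who will not switch are in the same position.

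The endpoint population is fixed at allocation, so these patients belong to the denominator. If a site follows 3.2.1, their status at first ctDNA detection is unknown. An analysis plan can choose a denominator, but it cannot recover a scan that was not done. Section 1.2.1 says that overt metastases were turning up more often than expected, so this rate is of real interest to the trial.

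There is also an ordering fault inside 11.1. Imaging is placed after the eligibility checklist has been completed and submitted, although the checklist confirms eligibility and eligibility depends on the scan.

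**Working it through.** The plan states no figure on this point, so there is none to reproduce. The check is a comparison of texts, followed by simple arithmetic on the endpoint.

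**1. Who is scanned**

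| Allocated patient | 11.7 note 6 | 3.2.1 and 11.1 |
|---|---|---|
| Accepts pembrolizumab | scanned on the ctDNA result | scanned after treatment consent |
| Declines pembrolizumab | scanned on the ctDNA result | not scanned |
| On capecitabine, will not switch | scanned on the ctDNA result | not scanned |

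If nobody declines, both rules scan the same patients.

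**2. Does the exception in 9.1 reconcile them?** It exempts assessments that belong to ctDNA surveillance or standard care. The surveillance schedule in 8.2 has no imaging row, and imaging appears only in the pre-treatment column of 11.7. The exception therefore does not clearly cover the scan, and it would not alter the explicit condition in 3.2.1 in any case.

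**3. Order within 11.1.** Criterion 7 of 9.2.1 requires staging scans free of distant metastases and local recurrence, and 9.3 makes a patient ineligible if the pre-treatment imaging shows macroscopic disease. A checklist that confirms eligibility cannot properly be completed before that imaging. The introduction to section 9 has the opposite order to 11.1: checks and assessments first, then notice to the trials unit.

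**4. Size.** Inputs: 150 patients in surveillance (19.1.1) and 30% ctDNA-positive within 12 months (19.1.2), so 0.30 × 150 = 45. Assume that all 45 are allocated to pembrolizumab, as under v6.0. With x metastatic cases seen and u patients unscanned, the rate lies between x/45 and (x + u)/45, a width of u/45.

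- u = 1: 1/45 = 2.2 points
- u = 5: 5/45 = 11.1 points
- u = 9: 9/45 = 20.0 points

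Only the figure per patient is free of an assumption about how many decline. If just the 30 in the original 2:1 table were allocated, it would be 1/30 = 3.3 points.

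**5. Illustration** (assumed: a true rate of 40% and 5 decliners).

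- Note 6 followed: 18/45 = 40.0% (exact 95% CI 25.7 to 55.7).
- 3.2.1 followed, scanned patients only: 16/40 = 40.0% (24.9 to 56.7).
- 3.2.1 followed, unscanned counted as negative: 16/45 = 35.6%.
- 3.2.1 followed, unscanned counted as positive: (16 + 5)/45 = 46.7%.

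With 9 decliners at the same rate, the limits are 14/45 = 31.1% and 23/45 = 51.1%.

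**6. Does an early scan fit the 4-week imaging window in 11.1?** Not always. Let a capecitabine patient be scanned on day 0 and stop capecitabine on day s. After the 4-week washout in 9.3, the first dose is on day s + 28 at the earliest. For any s above 0 the scan is then more than 28 days old. The same can happen when the start is delayed for the practical reasons that 9.3 allows.

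**The case against.** The strongest reply is that this is wording left behind by an amendment, with little effect. Note 6 refers expressly to v6.0, and the older sections were not updated to match. Registration criterion 12 (5.4.1) already requires willingness to take pembrolizumab on ctDNA detection, so decliners should be few. The endpoint is a descriptive secondary proportion, and the treatment of missing scans can be left to the analysis plan. Most of this stands and limits the weight of the point. It does not remove the conflict, because both rules are in the current text and a missing scan cannot be supplied later.

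It is also fair that not every text cited on consent contradicts note 6. Note 4 names no form and can be read as compatible with it, and 9.1 has its exception. Section 9 and 9.2 speak of pre-treatment assessments without naming imaging. The conflict rests on 3.2.1 and 11.1, with section 9 and 9.2 in support.

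Two stronger readings are tempting and are not supported:

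- A reader might infer that a decliner found to have metastases leaves the intention-to-treat set, while an unscanned one stays in and counts as a failure. In 19.4 the exception for recurrence qualifies ineligibility. Patients who do not want pembrolizumab are kept without qualification, so the text does not put a scanned decliner out.
- A reader might infer that, for patients who accept, the scan falls between day 0 and day 28 after notification. The extension in 9.3 allows a later first dose, and so a later scan.

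**Conclusion.** The concern holds as an inconsistency about who is scanned and when. Note 6 conflicts with 3.2.1 and 11.1, and 11.1 also places the scan after a checklist that depends on it. The consequence is confined to the secondary endpoint of overt metastases at first ctDNA detection: 2.2 percentage points undetermined for each unscanned patient, if all 45 planned positives are allocated. The total depends on the number of decliners, which the protocol does not give and which may be small; with none, the endpoint population is fully scanned under either rule. The A'Hern success criterion, alpha and power do not change, because 19.1.2 ties success to the number who start treatment. No firm claim is made about the intention-to-treat set. The point merits correction because the remedy is cheap and lost scans cannot be replaced.

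**What to change.** Make note 6 the single rule. Reword 3.2.1, the introduction to section 9, 9.2 and 11.1, and clarify 9.1 and note 4, so that the staging scan is done on confirmation of the positive ctDNA result, under the v6.0 registration consent, whatever the patient decides about pembrolizumab, and before the eligibility checklist is submitted.

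State in 11.1 what happens when the first dose falls more than 4 weeks after this scan, whether through capecitabine washout or a delay allowed by 9.3. Either the scan stays valid for a stated longer window, or it is repeated for eligibility. The first scan is used for the endpoint in both cases.

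In 19.3.2, keep the population as patients allocated to pembrolizumab, report the proportion among those scanned, and give the number not scanned. That count is also needed for patients allocated before v6.0, whom the registration consent in note 6 does not cover.

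The cost is text changes, scans for the few decliners (which note 6 already requires) and an occasional repeat scan. No new consent form is needed, because the v6.0 registration form already covers imaging.
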